- Subject reported AEs prior to or after surgery
- Eve Drop Burden Questionnaire
- Ocular Pain Assessment
- Anterior Chamber Cell Count

- Anterior Chamber Cell Flare
- Insert visualization

Day 28-35 (+/- 5 days from first eye sx)

- Medical history and concurrent illnesses
- Concomitant medications
- Distance VA
- MRX
- BCVA
- Ophthalmic examination (dilated fundus exam)
- Slit lamp Exam
- OCT
- IOP
- Subject reported AEs prior to or after surgery
- Eye Drop Burden Questionnaire
- Adapted COMTOL Questionnaire
- Ocular Pain Assessment
- Anterior Chamber Cell Count
- Anterior Chamber Cell Flare
- Insert visualization

Month 3 (+/- 7 days from first eye sx)

- Medical history and concurrent illnesses
- Concomitant medications
- Distance VA
- BCVA
- Slit lamp Exam
- IOP
- Subject reported AEs prior to or after surgery
- Ocular Pain Assessment
- Anterior Chamber Cell Count
- Anterior Chamber Cell Flare
- Insert visualization

Unscheduled Visits

All attempts should be made to keep patients on the study schedule. Unscheduled visits may be necessary to repeat testing following abnormal laboratory results, for follow-up of AEs, or for any other reason, as warranted.

Adverse Event Information Collection

The investigator (or designee) will record all AEs that occur during the study The definition of an AE and SAE, and information on the determination of severity and relationship to treatment are provided in Section 6.

Rescue Criteria

- Patients should be rescued at any time at the discretion of the investigator.
- The following rescue criteria are to be applied by the investigator:
 - > Grade 3 anterior chamber cells
 - Ocular pain score of > 5 due to ocular inflammation
- Patients requiring rescue therapy will be prescribed: topical steroid and topical NSAID per the discretion of the investigator.

If a patient requires rescue therapy in the eye containing the dexamethasone insert, the insert will not be removed, and subjects will be followed for safety.

Safety Definitions, Reporting, and Monitoring

Definitions

Adverse Event

An AE is any untoward medical occurrence in a patient administered a study drug which may or may not have a causal relationship with the study drug. Therefore, an AE is any unfavorable and unintended sign (including abnormal laboratory finding), symptom, or disease which is temporally associated with the use of a study drug, whether or not considered related to the study drug.

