An AE also includes any worsening (i.e. any clinically significant change in frequency and/or intensity) of a pre-existing condition that is temporally associated with the use of the study drug.

Serious Adverse Event

A SAE is any untoward medical occurrence that at any dose:

- Results in **death** includes all deaths, even those that appear to be completely unrelated to study drug (e.g. a car accident in which a patient is a passenger).
- Is **life-threatening** in the view of the investigator, the patient is at immediate risk of death at the time of the event. This does not include an AE that had it occurred in a more severe form, might have caused death.
- Requires in-patient **hospitalization** or prolongation of existing hospitalization. In-patient hospitalization is defined as admission to a hospital or an emergency room for longer than 24 hours. Prolongation of existing hospitalization is defined as a hospital stay that is longer than

was originally anticipated for the event, or is prolonged due to the development of a new AE as determined by the investigator or treating physician.

- Results in persistent or significant **disability/incapacity** (substantial disruption of one's ability to conduct normal life functions).
- Is a congenital anomaly/birth defect
- Is an **important medical event** Important medical events may not be immediately life-threatening or result in death or hospitalization, but may jeopardize the patient or may require intervention to prevent 1 of the other serious outcomes listed above (e.g., intensive treatment in an emergency room or at home for allergic bronchospasm; blood dyscrasias or convulsions that do not result in hospitalization; or development of drug dependency or drug abuse). Any malignancy (other than basal cell skin cancers) would be considered a medically important event.

Recording and Reporting Adverse Events

All AEs and SAEs will be recorded only if they are medically relevant.

All SAEs, regardless of assessment of causal relationship to study insert will be reported to Ocular Therapeutix.

To report an SAE, Ocular Therapeutix will be contacted at the following:

[contact]

SAE [contact]

The investigator will promptly report to the IRB all unanticipated problems involving risks to patients. This includes death from any cause and all SAEs related to the use of the study insert. All SAEs will be reported to the IRB, regardless of assessed causality.

Study Variables

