An appropriately constituted IRB, as described in ICH Guidelines for GCP, will review and approve:

- The protocol, ICF, and any other materials to be provided to the patients (e.g. advertising) before any patient may be enrolled in the study
- Any amendment or modification to the study protocol or ICF before implementation, unless the change is necessary to eliminate an

immediate hazard to the patients, in which case the IRB will be informed as soon as possible

Ongoing studies will be reviewed by the IRB/EC on an annual basis or at intervals appropriate to the degree of risk.

In addition, the IRB will be informed of any event likely to affect the safety of patients or the continued conduct of the clinical study.

A copy of the IRB approval letter will be sent to Ocular Therapeutix prior to shipment of drug insert supplies to the investigator. The approval letter will include the study title, the documents reviewed, and the date of the review.

Records of the IRB review and approval of all study documents (including approval of ongoing studies) will be kept on file by the investigator.

APPENDICES

Protocol Appendix A: Ease of use Survey

Protocol Appendix B: Eye Drop Burden Questionnaire

Protocol Appendix C: Adapted COMTOL

REFERENCES

1. DEXTENZA [PACKAGE INSERT]. BEDFORD, MA: OCULAR THERAPEUTIX, INC; 2019.

Protocol Appendix A: Ease of Use Survey

The investigator will grade the level of ease of insertion of the intracanalicular insert on a 0 to 10-point scale.

The Investigator will record ease of insertion procedure on the appropriate Case Report Form.

0 1 2 3 4 5 6 7 8 9 10

Very Easy

Very Hard

Protocol Appendix B: **Eye Drop Burden Questionnaire**

		Never	Rarely	Sometimes	Usually	Always
		1	2	3	4	5
1.	I forget to administer my eye drops.					
2.	It is difficult and/or frustrating to administer my eye drops.					
3.	My eye drops burn and/or sting when I administer them.					

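### Section 5.2.3 has every adverse event recorded, while Section 6.2 records only those judged medically relevant, a term the protocol never defines

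*Protocol*

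**What the plan says.** Two current sections of the protocol state a recording rule. (Section numbers here follow the table of contents, because most body headings are unnumbered.)

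- Section 5.2.3, Adverse Event Information Collection: "The investigator (or designee) will record all AEs that occur during the study".
- Section 6.2, Recording and Reporting Adverse Events: "All AEs and SAEs will be recorded only if they are medically relevant".

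The definition in Section 6.1.1 is broad: "An AE is any untoward medical occurrence in a patient administered a study drug", whether or not it is related to the drug. It sets a threshold in one situation only: "An AE also includes any worsening (i.e. any clinically significant change in frequency and/or intensity) of a pre-existing condition".

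Reporting of serious events carries no relevance condition. Section 6.2 says "All SAEs, regardless of assessment of causal relationship to study insert will be reported to Ocular Therapeutix" and "All SAEs will be reported to the IRB, regardless of assessed causality". Section 8.4 adds that "the IRB will be informed of any event likely to affect the safety of patients".

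**The concern.** Whether an event enters the record is decided at the visit. An event that is never written down cannot be recovered by any later analysis, so this is not a detail that can be left to a statistical analysis plan.

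The condition in Section 6.2 has no criterion. The title page lists a primary investigator and several sub-investigators, and Section 5.2.3 also allows a designee to record. Without a definition these people may apply different thresholds. The study is open-label and the two eyes of each patient are treated differently, so the judgement can be made with knowledge of which eye has the insert. What is at stake is the completeness and reproducibility of the non-serious safety record, not the validity of an efficacy comparison.

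**Working it through.** The protocol states no figure on this point and none can be derived, so the check compares the text.

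**1. Apply both rules to each kind of event.**

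| Event | Section 5.2.3 | Section 6.2 |
|---|---|---|
| Non-serious AE, judged relevant | record | record |
| Non-serious AE, judged not relevant | record | do not record |
| SAE, judged relevant | record | record and report |
| SAE, judged not relevant | record | recording sentence: do not record; reporting sentences: report |

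The second row is a direct contradiction. The fourth is awkward, but the reporting sentences cover all SAEs, so in practice serious events are still documented. The working conflict therefore concerns non-serious AEs judged not relevant.

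**2. Look for a definition that would remove the conflict.**

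- The phrase used in Section 6.2 appears nowhere else in the protocol.
- The AE definition has no general relevance threshold. Its one threshold applies to worsening of a pre-existing condition. For those events Section 6.2 adds a second, unexplained hurdle.
- The nearest wording is in Section 6.1.2: "Any malignancy (other than basal cell skin cancers) would be considered a medically important event". That is a criterion for seriousness. Used as the meaning of the filter, it would exclude every non-serious AE and make the mention of AEs alongside SAEs redundant. It cannot be the intended definition.
- Section 5.2.3 refers to Section 6 for severity and relationship to treatment. Section 6 contains no such rules, so they cannot stand in for the missing threshold.

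**3. Count what depends on the AE record.**

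- Listed endpoints: anterior chamber cell, pain, COMTOL preference, anterior chamber flare, IOP rise, CME, ease of insertion and eye drop burden. Of these 8, the number that are AE counts is 0.
- Assessments at Day 90 that do not pass through the filter, where Table 1 and the Month 3 list agree: distance VA, BCVA, slit lamp, IOP, pain, cell, flare and insert visualization, which makes 8.
- Collected at Day 30 but not repeated at Day 90 in Table 1: dilated fundus examination, OCT, COMTOL and Eye Drop Burden, which makes 4.
- Subject-reported AEs are a scheduled item at all 7 visits after baseline, with no relevance condition. The visit schedule thus sides with Section 5.2.3, and Section 6.2 is the outlier.

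**The case against.** The strongest reply accepts the contradiction and disputes its importance. The condition in Section 6.2 may be no more than an informal wish to keep trivia off the forms, and if staff count every AE as relevant, nothing is lost. SAE reporting is unfiltered, and so is the duty to tell the IRB of events that bear on patient safety. IOP, OCT, slit lamp findings, pain, cell, flare and surgical complications are collected in their own right. Patients are asked about AEs at every visit after baseline, which narrows the gap further. Nor would deleting the clause remove unmasked judgement, because deciding what is untoward, or what counts as a clinically significant worsening, is also done unmasked.

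Most of this stands as a limit on consequence. The harm is conditional: following Section 6.2 can leave the record incomplete, but need not. The open-label point is secondary, since deletion removes one unmasked judgement and leaves others.

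None of it reconciles the two sentences. If the condition was meant as a filter for trivia, Section 5.2.3 is wrong and must change. The subject-reported item shows that the protocol means to collect events beyond the fixed examinations, and Section 6.2 then allows those same events to be dropped. The examinations are also tied to visits: after Day 7 the next scheduled visits are Day 30 and Day 90, and COMTOL asks about a fixed list of symptoms once.

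**Conclusion.** The concern holds. Sections 5.2.3 and 6.2 give opposite instructions for a non-serious AE judged not medically relevant, and nothing in the protocol defines the term or settles which section prevails. The conclusion rests on the wording alone and needs no numerical assumption.

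The extent of under-recording cannot be estimated from the documents. What can be said is where it would fall: on non-serious events that the scheduled examinations, the COMTOL interview, the record of surgical complications and the concurrent-illness entries do not capture. With no AE count among the 8 endpoints, the efficacy comparison is not threatened. The point should be fixed because the contradiction is certain, it affects safety documentation and the repair is small.

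**What to change.** In Section 6.2, delete the condition on medical relevance so that the sentence requires all AEs and SAEs to be recorded. It then agrees with Section 5.2.3, the AE definition and the scheduled subject-reported AE item.

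The other consistent repair is to keep a filter, define it, confine it to non-serious AEs and rewrite Section 5.2.3 to match. That takes more edits and keeps an additional unmasked judgement in the recording step, so deletion is preferable.

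Deletion changes one clause in one sentence. Its downside is probably a few more minor AE entries across 30 patients.

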Dextenza's ability to treat post-operative inflammation while also increasing remaining tear volume by punctal occlusion has potential to improve visual outcomes for patients while also decreasing post-operative drop inconvenience. The studied patient population is having their initial cataract evaluation and surgery on the same day, decreasing patient inconvenience, adding Dextenza is another arrow in the quiver.

Rationale for Study Design

This prospective contralateral eye study will compare the outcomes of 30 patients undergoing cataract surgery. All eyes will receive intracameral DMK at the conclusion of surgery. All eyes will be treated with Vigamox 0.5% QID for 1 week and Prolensa

(bromfenac 0.07%) QD for 1 month. After randomization, one eye per patient will receive Dextenza in place of topical steroid while the other eye has topical prednisolone acetate 1% QID 1 week, TID 1 week, BID 1 week, and QD 1 week. The primary endpoints of anterior chamber cell and mean pain score correlate to the initial FDA approval trial for Dextenza. The study inclusion and exclusion criteria were chosen based on patients who normally would be successful with cataract surgery, including the absence of pre-existing intraocular inflammation or macular edema. The study follow-up visits were based on the Vance Thompson Vision standard postoperative follow-up protocols.

Study Objectives

Primary Objective

To determine the effect of dexamethasone intracanalicular insert through Week 4 as measured by:

- Mean anterior chamber cell score as measured by Slit Lamp Biomicroscopy evaluation using grading scale of 0 to 4 + (SUN Working Group Grading Scheme) at post-op Day 1, Day 7, and Week 4.
- Mean pain score as measured by Visual Analog Score numerical grading scale 0-10 at post-op Day 1, Day 7, and Week 4.

To determine patient preference through Week 4 as measured by:

• Adapted COMTOL Questionnaire at Week 4.

Secondary Objectives

To determine the effect of dexamethasone intracanalicular insert through Week 4 or 12:

- Mean anterior chamber flare score as measured by Slit Lamp Biomicroscopy evaluation using grading scale of 0 to 4 + (SUN Working Group Grading Scheme) at post-op Day 1, Day 7, and Week 4.
- Incidence of increased intraocular pressure (IOP) >10mmHg above baseline as measured by Goldmann Applanation Tonometer at post-op Day 1, Day 7, and Week 4.
- Incidence of Cystoid Macular Edema (CME) as measured by optical coherence tomography (OCT) at post-op Week 4.

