To determine physician ease of insertion following dexamethasone intracanalicular insert placement prior to same-day surgery as measured by:

• Physician Ease of Use Survey following dexamethasone intracanalicular placement on Surgical Visit Day 0.

To determine eye drop therapy burden on the patient through Week 4 as measured by:

• Eye Drop Burden Questionnaire at post-op Day 7 and Week 4.

Study Design

Study Description and Duration

This prospective, open-label, randomized, investigator-sponsored clinical study seeks to investigate a new protocol for in-clinic Dextenza insertion by optometrists at the day of surgery. This three month study will study the clearance of intraocular pain and inflammation comparing topical steroids versus Dextenza.

Selection, Withdrawal, and Replacement of Patients Study Population

The study aims to enroll 30 patients undergoing routine sequential bilateral cataract surgery.

Inclusion Criteria

A patient's study eye must meet the following criteria to be eligible for inclusion in the study:

- Patients 18 years of age or older, undergoing routine, uncomplicated, sequential bilateral cataract surgery.
- Willing and able to comply with clinic visits and study related procedures
- Willing and able to sign the informed consent form

Exclusion Criteria

A patient who meets any of the following criteria will be excluded from the study:

- Patients under the age of 18.
- Patients who are pregnant (must be ruled out in women of child-bearing age with pregnancy test).
- Active infectious ocular or systemic disease.
- Patients with active infectious ocular or extraocular disease.
- Patients actively treated with local or systemic immunosuppression including systemic corticosteroids.
- Patients with known hypersensitivity to Dexamethasone.
- Patients with severe disease that warrants critical attention, deemed unsafe for the study by the investigator.
- Patients with proliferative diabetic retinopathy or uncontrolled diabetes as deemed by an A1C > 10.0.
- Patients with a history of ocular inflammation or macular edema.
- Patients with a pre-existing epiretinal membrane (ERM)
- Patients with allergy or inability to receive intracameral antibiotic.
- Patients on systemic non-steroidal anti-inflammatory drugs (NSAID) greater than 1,200 mg/day

• Patients with a corticosteroid implant (i.e. Ozurdex).

Treatment Logistics and Accountability Packaging, Labeling, and Storage

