4.	My eye drop treatment interferes with the daily activities of my life.					
5.	I forget to wash my hands prior to administering my eye drops.					
6.	I accidentally administer more and/or less than one eye drop to the eye.					
7.	The drops miss my eye when I administer them.					
8.	The bottle tip touches my eye when using my eye drops.					
	Add up the numbers Score.	for each sta	tement to ca	lculate the total	l Eye Drop B	Burden
	Total Eye Drop Bure	den Score =				
	Low Eye Drop Burd Moderate Eye Drop High Eye Drop Burd	Burden: 19-	29			

Protocol Appendix C: Adapted COMTOL

Comparison of Ophthalmic Medications for Tolerability (COMTOL) Questionnaire (adapted to compare physician & patient administered 'fewer-drops' regimen ((Treatment A- Experimental Group)) to patient-only administered total topical therapy ((Treatment B- Control Group)).

Interviewer: Please read the following verbatim!

Thank you for participating in our study. Your evaluation of the test "fewer-drops" treatment (Treatment A- Experimental Group) that the surgeon and you administered following your surgery compared to the total eyedrops (Treatment B- Control Group) you administered following surgery is most valuable to us. We would greatly appreciate your assistance by answering the following questions as best as possible. All answers are confidential.

Every patient received both treatment regimens. Every patient received Treatment A in one eye and Treatment B in the opposite eye. For clarification, here are the definitions of each treatment group:

Treatment A (Experimental Group-fewer-drops, physician & patient administered):

• Dextenza (steroid punctal plug/insert) + Vigamox drops 4x/day for 1st week + Prolensa drops 1x/day for one month

Treatment B (Control Group- total topical eyedrop therapy, patient-only administered):

- Prednisolone drops 4x/day for 1st week, 3x/day for 2nd week, 2x/day for 3rd week, 1x/day for 4th week + Vigamox drops 4x/day for 1st week + Prolensa drops 1x/day for one month
- 1. (Interviewer: Questions 1 and 2 are to be asked only at the Month 1 Visit).

Now that you tried both test regimens, did you prefer the Treatment A (fewer-drops, physician & patient administered) regimen or the Treatment B (total eyedrop therapy, patient-only administered) regimen?

(Interviewer: Please check the appropriate response below).
Treatment A regimen (Experimental Group-fewer drops
Treatment B regimen (Control Group-all drops)
Neither (Do not read)

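### Adapted COMTOL: the preference question names Treatment A first for every patient, so an order effect cannot be separated from preference; some routing and one introductory sentence also need correction

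*Protocol*

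**What the plan says.** **Status of preference.** Study Objectives, Primary Objective, includes "To determine patient preference through Week 4 as measured by" the Adapted COMTOL at Week 4. The synopsis also lists it among the primary endpoints. Thirty patients are planned, each receiving both regimens, one per eye.

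**The script.** Protocol Appendix C tells the interviewer to read the text verbatim. An introduction comes first, then the sentence "here are the definitions of each treatment group" with both full drop schedules, then Question 1: "did you prefer the Treatment A (fewer-drops, physician & patient administered) regimen or the Treatment B (total eyedrop therapy, patient-only administered) regimen". Treatment A precedes Treatment B at all three places. No version with the order reversed is given.

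**Placement.** The introduction describes Treatment A as something "that the surgeon and you administered following your surgery". Study Description and Duration describes "a new protocol for in-clinic Dextenza insertion by optometrists at the day of surgery". The ease-of-insertion objective speaks of "dexamethasone intracanalicular insert placement prior to same-day surgery as measured by" a survey on Day 0. The synopsis likewise has the optometrist place the insert in the office before surgery.

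**Routing.** In the Treatment B half, Question 10 sends a patient without side effects to Question 10. Questions 11 and 12 both point the interviewer to Question 7. Question 1 allows an unread answer 'Neither', but Questions 2 and 18 ask about the preferred regimen with no skip for that answer.

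**The concern.** In a two-option question put to a patient by an interviewer, being named first may in itself raise or lower the share choosing an option. When the order never varies, that effect and true preference are completely confounded. No analysis can undo this, because it depends on the words the patients heard. It is therefore a matter for the script in the protocol and cannot be left to the SAP. At stake is the reading of a measure that the protocol places under its Primary Objective.

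The other two matters are separate. The routing errors leave the Treatment B side-effect items without the correct written path that the matching Treatment A items have, in a form meant to compare the two. The introductory sentence conflicts with the protocol body on the very feature under study, namely who places the insert and when.

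**Working it through.** The protocol states no expected preference share, alpha or power for this measure, so there is no figure of its own to reproduce.

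**1. What a fixed order leaves in the result.** Inputs: 30 patients (synopsis) and A named first for all (Appendix C). Let being named first change A's share by dA points and B's share by dB points, of either sign. Both are unknown; the values below are assumptions for scale. Suppose n1 patients hear A first and n2 hear B first, n1 + n2 = 30, and every patient chooses A or B. Then

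bias in A's share = (n1 × dA − n2 × dB) / 30.

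- Fixed order, 30/0: bias = dA. For 2, 5 and 10 points this is 30 × 0.02 = 0.6, 30 × 0.05 = 1.5 and 30 × 0.10 = 3 patients.
- Alternation 15/15, dA = dB: bias = 0.
- Alternation 16/14, dA = dB = d: bias = 2d/30, that is 0.13, 0.33 and 0.67 points for d = 2, 5 and 10.
- Alternation 15/15, dA and dB unequal: bias = (dA − dB)/2. For 10 and 4 points, (10 − 4)/2 = 3 points remain, against 10 under the fixed order.

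Alternation is not better for every conceivable pair: with dA = 2 and dB = 10 it leaves (2 − 10)/2 = −4 points, against 2 under the fixed order. For positive dA it leaves less than the fixed order whenever dB lies between −dA and 3 × dA.

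**2. How well the order effect could be measured.** With 15 patients per order and a 50% share, the 95% half-width for the difference between orders is 1.96 × √(2 × 0.25/15) = 0.358, about 36 points. Alternation balances the effect; it does not estimate it usefully.

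**3. Are the tags false?** Drops per eye from the schedules in Appendix C, with a month taken as 30 days:

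- Prednisolone: 7 × (4 + 3 + 2 + 1) = 70; Vigamox: 4 × 7 = 28; Prolensa: 30.
- Treatment A: 28 + 30 = 58. Treatment B: 58 + 70 = 128.
- With a month of 28 to 31 days: 56 against 126, up to 59 against 129.

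The 'fewer-drops' tag is true, it follows from the definitions just read, and B carries a matching tag.

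**4. Routing, half against half.**

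| Function | Treatment A half | Treatment B half as written | Matching target |
|---|---|---|---|
| No side effects: go to | Q3 → Q6 | Q10 → Q10 (itself) | Q13 |
| Frequency item refers to | Q4 → Q3 | Q11 → Q7 | Q10 |
| Bother item refers to | Q5 → Q4 | Q12 → Q7 | Q11 |

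Question 7 is the Treatment A half's list of daily activities, not a side-effect list. So three references are wrong. The text around Questions 7 to 9 and 14 to 16 is too broken in the copy at hand to compare.

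**5. Placement.** The introductory sentence names the surgeon and the patient, and a time after surgery. The protocol body names optometrists, in clinic, before same-day surgery. Treatment A as defined also includes Vigamox and Prolensa drops. A time after surgery, and administration by the patient, fit those drops but not the insert. The intracameral injection does not explain the word 'surgeon', because both eyes receive it.

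**The case against.** By Week 4 every patient has used both regimens, and both schedules are read out immediately before Question 1. A preference formed from experience may be little affected by which option is named first, and the documents give no evidence of any order effect. The first eye's treatment is randomized, so the sequence of treatments is already balanced by design. The Rationale for Study Design names only cell and pain as primary endpoints. The routing errors are clerical: the spoken wording of Questions 11 and 12 directs the patient to what was just said, and an interviewer can readily handle 'Neither'.

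Most of this stands, and it limits the weight of the point. It does not remove it. Randomizing the eye leaves the interview order fixed, and preference is listed under the Primary Objective whatever the rationale emphasises. The arithmetic above shows what a fixed order would carry through, not that an effect exists.

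A reader might infer more: that the 'fewer-drops' tag leads patients towards A and so biases the primary result. The documents do not support that. The tag is accurate, matched by B's tag and already known to patients in an open-label trial. Preferring A because it needs fewer drops is a valid answer.

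**Conclusion.** The order point holds as an inexpensive improvement to a measure listed under the Primary Objective. Its size and direction are unknown. The figures of 0.6 to 3 patients rest on assumed effects of 2 to 10 points and are for scale only. Full cancellation needs equal order effects for the two regimens and equal numbers per order; with equal numbers but unequal effects, (dA − dB)/2 remains.

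Removing the tags is optional, since no bias from them is shown.

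The three wrong references and the missing 'Neither' skip are certain from the text. A reader might take them as compromising the preference result, but they affect the tolerability and follow-up items and leave the Question 1 answer untouched.

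The introductory sentence is partly right, for the patient's own drops. For the insert it conflicts with the protocol body, and the texts must be reconciled. Nothing shows that it changes the preference answer.

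**What to change.** - **Order.** Alternate across patients which regimen is named first in the introduction, the definitions and Question 1, and record the order used. This needs two script versions and one extra recorded item.
- **Tags (optional).** Drop 'fewer-drops' and 'total eyedrop' from Question 1 and keep the full definitions read just before it.
- **Routing.** Send 'none' in Question 10 to Question 13. Refer Question 11 to Question 10, and Question 12 to Question 11. Add a skip past Questions 2 and 18 for 'Neither'.
- **Placement.** Reconcile the introductory sentence with the protocol body so that both give the same account of who places the insert and when.

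All of this fits in a single form revision with IRB approval. Sample size, visits and the other assessments do not change.
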